3 OBJECTIVES AND ENDPOINTS

OBJECTIVES		ENDPOINTS	Л	USTIFICATION FOR ENDPOINTS	
Primary					
 Dose escalation: To evaluate the safety and tolerability of L9LS administered at 300 mg and 600 mg SC and 20 mg/kg IV in healthy Malian adults, and at 150 mg and 300 mg SC in healthy Malian children. Efficacy: To evaluate the safety and tolerability of L9LS administered at 150 mg and 300 mg SC in healthy Malian children. 	2.	Dose escalation and efficacy: Incidence and severity of local and systemic AEs occurring within 7 days after the administration of L9LS. Efficacy: Pf blood-stage infection as detected by microscopic examination of thick blood smears obtained between 1 week and 24 weeks after administration of L9LS or placebo.	2.	Assessment of AEs is a standard measure of study agent safety and tolerability. Blood smear is the gold standard for diagnosis of blood-stage Pf infection.	
3. Efficacy: To determine if SC administration of L9LS at 150 mg and 300 mg (compared to placebo) mediates protection against naturally occurring Pf infection in healthy Malian					

Version Date: 14 March 2024

children during a single malaria season as detected from microscopic examination of thick blood smear.

Secondary (to be addressed using data from both parts of the study)

- 1. To evaluate the PK of L9LS throughout the study at dose levels of 300 mg and 600 mg SC and 20 mg/kg IV in healthy Malian adults, and at 150 mg and 300 mg SC in healthy Malian children, and to correlate L9LS serum concentration with Pf infection risk.
- 2. To determine if SC administration of L9LS at 150 mg and 300 mg (compared to placebo) mediates protection against naturally occurring Pf infection in healthy Malian children during a single malaria season as detected by RT-PCR.
- 3. To determine if SC administration of L9LS at 150 mg and 300 mg (compared to placebo) mediates protection against clinical malaria in healthy Malian children during a single malaria season as defined by an illness accompanied by measured axillary fever ≥37.5°C, or history of fever (subjective or objective) in the previous 24 hours, and Pf asexual parasitemia >5,000 parasites/µL as detected from microscopic examination of thick blood smear.
- 4. To determine if SC administration of L9LS at 150 mg and 300 mg (compared to placebo) mediates protection against clinical malaria in healthy Malian children during a single malaria season as defined

- 1. Measurement of L9LS in sera of recipients.
- 2. Pf blood-stage infection as detected by RT-PCR for 28 weeks after administration of L9LS or placebo in the dose escalation study and for 24 weeks after administration of L9LS or placebo in the efficacy study.
- 3. Incidence of clinical malaria (definition 1, see section 2.2.2.3) for 28 weeks after administration of L9LS or placebo in the dose escalation study and for 24 weeks after administration of L9LS or placebo in the efficacy study.
- 4. Incidence of clinical malaria (definition 2, see section 2.2.2.3) for 28 weeks after administration of L9LS or placebo in the dose escalation study and for 24 weeks after administration of L9LS or placebo in the efficacy study.
- 5. PK analysis of L9LS and the association of L9LS concentration with Pf infection risk.
- 6. PK analysis of L9LS and the association of L9LS concentration with clinical malaria risk.

- Concentrations of L9LS in blood will help assess durability of L9LS at each dose level.
- 2. RT-PCR is more sensitive than blood smear for detecting Pf blood-stage infection.
- 3. 6–10-year-old children in Mali are at high risk for clinical malaria.
- 4. 6–10-year-old children in Mali are at high risk for clinical malaria.
- Concentrations of L9LS in blood will help assess durability of L9LS and will allow for correlation with Pf infection risk.
- 6. Concentrations of L9LS in blood will help assess durability of L9LS and will allow for correlation with clinical malaria risk.

Version Date: 14 March 2024

by an illness accompanied by any level of Pf asexual parasitemia as detected from microscopic examination of thick blood smear that results in the administration of anti-malarial treatment.

- 5. To evaluate the PK of L9LS throughout the study at the dose of 150 mg and 300 mg and to correlate L9LS serum concentration with Pf infection risk.
- 6. To evaluate the PK of L9LS throughout the study at the dose of 150 mg and 300 mg and to correlate L9LS serum concentration with clinical malaria risk.

Tertiary/Exploratory

- 1. To determine whether ADA to L9LS can be detected in sera of recipients at specific timepoints throughout the study.
- 2. To assess for IgG1 allotypes and allotype-specific effects on L9LS PK.
- 3. To explore and characterize the cellular immune response to L9LS.
- 4. To determine if the efficacy of L9LS is specific to certain Pf parasite genotypes at the CSP locus.
- 5. To explore the impact of pre-existing parasitemia on the protective efficacy and PK of L9LS.
- 6. To explore the impact of pre-existing CSP antibodies on the protective efficacy and PK of L9LS.

- 1. Measurement of ADA to L9LS in sera of recipients.
- 2. Assessment of IgG1 allotypes and allotypes specific effects on L9LS PK.
- 3. Characterization of the cellular immune response to L9LS.
- 4. CSP genotyping of parasites isolated from study subjects.
- 5. Pre-existing parasitemia detected by microscopic examination of thick blood smears or RT-PCR before L9LS administration.
- 6. Pre-existing CSP-specific antibodies measured in sera collected before L9LS administration.

- ADA to L9LS may impact the PK and activity of L9LS.
- 2. Subject IgG1 allotype may impact the PK and activity of L9LS.
- 3. L9LS-induced cellular immune responses may be associated with Pf infection risk.
- 4. L9LS efficacy may be specific to certain Pf parasite genotypes at the CSP locus.
- 5. Pre-existing parasitemia may impact the protective efficacy and PK of L9LS.
- 6. Pre-existing
 CSP-specific antibodies
 may impact the
 protective efficacy and
 PK of L9LS.

Extension Phase Primary

Version Date: 14 March 2024

- 1. To evaluate the safety and tolerability of a second SC dose of L9LS administered at 150 mg and 300 mg (compared to placebo) in healthy Malian children.
- 2. To evaluate the PK of L9LS throughout the study at dose levels of 150 mg and 300 mg SC in healthy Malian children.
- 3. To determine if ADAs to L9LS can be detected in sera of recipients at specific timepoints throughout the study and to correlate the occurrence of ADAs with L9LS PK.

- 1. Incidence and severity of local and systemic AEs occurring within 7 days after the administration of L9LS.
- 2. Measurement of L9LS in sera of recipients.
- 3. Measurement of ADA in sera of recipients.
- 1. Assessment of AEs is a standard measure of study agent safety and tolerability.
- 2. Concentrations of L9LS in blood will help assess durability of L9LS at each dose level
- 3. ADA to L9LS may impact the PK and activity of L9LS.

Extension Phase Exploratory (see Figure 3 for study arm definitions)

- 1. To assess the efficacy of a second SC dose of L9LS at 150 mg and 300 mg (compared to placebo) in mediating protection against Pf infection and clinical malaria in healthy Malian children during a second malaria season (arms 1a vs. 1b; arms 2a vs. 2b), and to assess if this efficacy is influenced by whether or not a prior dose of L9LS was administered in year 1 (arms 1a vs. 3b; arms 2a vs. 3b).
- 2. To assess the efficacy of a first SC dose of L9LS at 150 mg or 300 mg (compared to placebo) in mediating protection against Pf infection and clinical malaria in healthy Malian children during the second malaria season (arms 3a vs. 3b).
- 3. To assess the risk of clinical malaria in children who received L9LS in year 1 but not year 2 (compared to children who received placebo both years; arms 1b vs. 3b; arms 2b vs. 3b).

- 1. Pf blood-stage infection as detected by microscopic examination of thick blood smears obtained between 1 week and 28 weeks after administration of L9LS or placebo.
- 2. Pf blood-stage infection as detected by RT-PCR from dried blood spots obtained between 1 week and 28 weeks after administration of L9LS or placebo.
- 3. Incidence of clinical malaria (definition 1, see section 2.2.2.3) between 1 week and 28 weeks after administration of L9LS or placebo.
- 4. PK analysis of L9LS and the association of L9LS concentration with Pf infection risk.
- PK analysis of L9LS and the association of L9LS concentration with clinical malaria risk.

- Blood smear is the gold standard for diagnosis of blood-stage Pf infection.
- 2. RT-PCR is more sensitive than blood smear for detecting Pf blood-stage infection.
- 3. 6–10-year-old children in Mali are at high risk for clinical malaria.
- 4. Concentrations of L9LS in blood will help assess durability of L9LS and will allow for correlation with Pf infection risk.
- 5. Concentrations of L9LS in blood will help assess durability of L9LS and will allow for correlation with clinical malaria risk.

Version Date: 14 March 2024

4. To evaluate the PK of L9LS
throughout the study at the dose
of 150 mg and 300 mg and to
correlate L9LS serum
concentration with Pf infection
risk.

5. To evaluate the PK of L9LS
throughout the study at the dose
of 150 mg and 300 mg and to
correlate L9LS serum
concentration with clinical
malaria risk.

4 STUDY DESIGN

4.1 Overall Design

This is a two-part, phase 2 trial evaluating the safety and tolerability of one-time SC or IV administration of L9LS in healthy Malian adults and one-time SC administration of L9LS in healthy Malian children, as well as its protective efficacy against naturally occurring Pf infection over a 7-month malaria season in healthy Malian children 6-10 years of age. The primary study hypotheses are that L9LS administered prior to the malaria season will be safe and will produce protection against malaria infection. Before study agent administration, all subjects will be given artemether-lumefantrine to clear any preexisting Pf blood-stage infection. Interim safety data from the ongoing VRC phase 1 trial of L9LS will be regularly reviewed, and if needed, the protocol and relevant study documents will be amended to reflect any new information.

The study will recruit from 2 MRTC clinics, 1 in Torodo and 1 in Kalifabougou. All of the screening, day 0, and day 14 visits will take place at Kalifabougou for all subjects, regardless of residence. The rural village of Kalifabougou is situated 46 km from the MRTC laboratory in Bamako where biological samples collected for this protocol will be processed and stored. Torodo is located 12 km north of Kalifabougou. The economy is based on subsistence farming. Kalifabougou and Torodo are similar in terms of geographic, demographic, and epidemiological characteristics, and both typically experience intense seasonal Pf transmission from June through December each year. ²⁵ Based on data collected in Kalifabougou, approximately 85% of children aged 6-10 years who are uninfected (PCR negative) before the malaria season become infected with Pf during the ensuing malaria season (Figure 5). ²⁵

Version Date: 14 March 2024

[figure not shown]

Figure 5. Kaplan-Meier plots, stratified by age for time to first *Pf* infection by PCR during the malaria season in Kalifabougou, Mali (ClinicalTrials.gov Identifier: NCT01322581).

The first part of the study is an age de-escalation and dose-escalation study for safety and tolerability. Adult subjects (N=18) in the dose-escalation study will be assigned in open-label fashion to 1 of 3 L9LS dose arms (n=6 for each dose level). Dosing will begin in the lowest dose arm (300 mg SC). Once all subjects in that arm reach day 7 post-administration, if no safety concerns have arisen, dosing will begin at the next dose level (600 mg SC). Once all subjects in that arm reach day 7 post-administration, if no safety concerns have arisen, dosing will begin at the highest dose level (20 mg/kg IV). Once all adult subjects reach day 7 post-administration, if

Version Date: 14 March 2024

no safety concerns have arisen, 18 subjects aged 6-10 years will be randomized 1:1 in double-blind fashion to 150 mg of L9LS versus placebo administered SC. Once all 18 subjects reach day 7 post-administration, if no safety concerns have arisen, an additional 18 subjects aged 6-10 years will be randomized 1:1 to 300 mg of L9LS versus placebo administered SC. Randomization of subjects aged 6-10 years in each L9LS dose arm will be weight-stratified (26-30 kg, n=6; 20-25 kg, n=6; 15-19 kg, n=6) and enrollment will be weight de-escalated starting with subjects weighing 26-30 kg. All subjects will be followed for safety to assess AEs at study visits over 28 weeks. Primary study assessments include medical history, physical examination and blood collection for identification of Pf infection and other research laboratory evaluations. After the last 6-year-old subject in the 300-mg L9LS arm reaches day 7 safety follow-up, an interim safety evaluation will be performed before enrollment begins for the efficacy part of the study. Data from the 36 subjects aged 6-10 years enrolled in the dose-escalation study will be included in a secondary analysis to determine the relationship between L9LS concentrations and the risk of Pf infection. For these 36 subjects, blinding will be maintained for treatment assignment (L9LS versus placebo), but not for possible L9LS dose group.

The second part of the study is a weight-stratified, randomized, double-blind, placebo-controlled trial to assess safety and protective efficacy of L9LS and placebo in children 6-10 years of age. In this part of the study, 225 subjects will be randomized 1:1:1 to SC administration of 150 mg of L9LS (n=75), 300 mg of L9LS (n=75), or placebo (n=75). Randomization of subjects in each arm will be weight-stratified (26-30 kg, n=75; 20-25 kg, n=75; 15-19 kg, n=75). Subjects in the efficacy study will receive the study agent and be followed at study visits over 24 weeks. Primary study assessments include medical history, physical examination, and blood collection for identification of Pf infection and other research laboratory evaluations.

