4.3 Justification for Dose

The doses used in this study were selected based on preclinical data and data generated in the ongoing phase 1 VRC study, which tested the dose range included in this protocol. This study will test fixed doses of L9LS in children in a defined range of subject weights to approximate the weight-based dosing used in the phase 1 VRC study. Compared to weight-based dosing, fixed dosing will provide a greater range of antibody concentrations in vivo for determining a protective L9LS titer. Fixed dosing is also simpler to administer, reduces the risk of medication errors, and is generally more cost effective—factors that are relevant to the potential use of L9LS in malaria-endemic regions.

Version Date: 14 March 2024

In the safety study, subjects aged ≥18 years weighing 60 kg or less will receive a SC dose of 300 mg (2 mL) or 600 mg (4 mL), approximating the weight-based dosing of 5 mg/kg and 10 mg/kg, respectively, in a 60-kg adult. An additional group of subjects aged ≥18 years weighing 60 kg or less in the safety study will receive an IV dose of 20 mg/kg. This dose will be administered IV rather than SC because 4 mL is the maximum volume of L9LS that will be administered SC in this study. In Kalifabougou, the average weight of adult females and males is 55.6 kg and 61.7 kg, respectively. In the safety and efficacy studies, subjects aged 6-10 years weighing ≥15 kg and ≤30 kg will receive a dose of 150 mg or 300 mg SC, approximating the weight-based dosing of 5 mg/kg and 10 mg/kg, respectively, in a 30-kg child, and 10 mg/kg and 20 mg/kg, respectively, in a 15-kg child. Based on recent data from the study site, approximately 85% of children aged 6-10 years in Kalifabougou weigh between 15 kg and 30 kg. The doses used in the efficacy study will complement the data generated in the ongoing phase 1 VRC study. The doses used in the phase 1 VRC study were derived from 1) efficacy data from the challenge studies performed in mice showing that the protective concentration of antibody in vivo is between 5-100 µg/mL in 2 different mouse models of malaria infection; 11 and 2) PK data from nonhuman primate studies with L9LS and prior clinical experience in healthy adults with human MAbs targeting HIV (i.e., VRC01, VRC01LS, and VRC07-523LS) and ebolavirus (MAb114) at the same dose.

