9.5 Statistical Analyses

9.5.1 General Approach

In general, descriptive statistics will be tabulated by treatment arm for endpoints of interest. This will include point estimates (mean, geometric mean, median, or proportions) and their respective 95% CIs. Formal comparisons will use standard methods, contingency tables for categorical variables, t-tests for comparing means if data follow a normal distribution or geometric means if data after log transformation follow a normal distribution, or nonparametric analogs for comparing medians. Unless specified in the subsequent sections, comparisons will be two-sided with type I error rate of 0.05.

Missing data will be considered as "missing completely at random" provided the amount of missing data is modest (e.g., <10%). We will examine the "missing completely at random" assumption if the amount of missing data is more than 10%. If the assumption does not hold, missing data will be handled under the "missing at random" assumption (that is, missingness depends only on observed variables) via methods such as multiple imputation and inverse propensity weighting. To handle the possibility of "missing not at random," a sensitivity analysis will be performed by imputing missing binary observations with the observed proportion in the opposite arm. A secondary sensitivity analysis will be considered by imputing missing binary observations as failures.

Version Date: 14 March 2024

Randomization: Weight-stratified randomization will be implemented in the dose-escalation study and the efficacy study. In the efficacy study, 75 participants will be recruited into each weight group (15-19 kg, 20-25 kg, and 26-30 kg). Within each weight group, randomization will be 1:1:1 allocation to the 2 L9LS arms and the placebo arm. The total number of participants will be 75 in each arm (25 of weight 15-19 kg, 25 of weight 20-25 kg, and 25 of weight 26-30 kg). A similar stratified randomization will be applied to the dose-escalation study: six participants in each weight group, starting with 26-30 kg, followed by 20-25 kg, and then 15-19 kg, will be recruited and randomized 1:1 to receive L9LS at the dose of 150 mg or placebo; if no safety concerns arise, randomization into the L9LS at the dose of 300 mg or placebo ensues in the same manner. To limit the number of dropouts before L9LS administration, randomization and L9LS administration will occur as close in time as possible.

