Since this trial adopts weight-stratified randomization, participants cover the dose range from 5 mg/kg to 20 mg/kg. In addition to the above efficacy analyses that compare each dose arm with the placebo arm, an exploratory analysis will be additionally conducted to assess how dosage, in terms of mg of L9LS per kg of subject body weight, affects the protective efficacy.

The above analyses will apply to both the primary and the secondary efficacy endpoints.

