9.5.5 Safety Analyses

Safety analysis will be primarily MITT where individuals who receive assignment but do not receive any product are excluded. Because of blinding and the brief length of time between assignment and administration, such cases will be very few. In the rare case of subjects receiving a regimen different from assignment, an as-treated analysis will be additionally performed where subjects will be analyzed according to the product they actually receive.

Safety data will be presented by line listing and tables at the individual level to provide details on safety events such as severity, duration, and relationship to study product. The number and percentage of subjects with 1 or more AE(s) will be summarized by dose arm along with the exact 95% CIs of the AE rate. The number and percentage of subjects under each AE will be

Version Date: 14 March 2024

additionally reported. For subjects experiencing more than 1 AE, the subjects will be counted once under the event of highest severity.

In the efficacy study, comparisons between the dose arms and the control arm will be additionally performed in terms of the proportions of solicited AEs, related AEs, and SAEs.

In the rare case of subjects receiving a regimen different from assignment, a per-protocol analysis will be performed as a secondary analysis, which will include subjects according to the product they actually receive in the study.

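### Adverse events are summarised and compared by treatment arm only, so no planned summary shows safety in the children who receive the highest mg/kg

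*Combined protocol and SAP*

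**What the plan says.** Section 4.1 sets three weight bands (26-30, 20-25 and 15-19 kg). In the paediatric dose-escalation part there are six children per band at each dose, allocated 1:1, and "enrollment will be weight de-escalated starting with subjects weighing 26-30 kg". For the efficacy part, "Randomization of subjects in each arm will be weight-stratified"; Section 9.5.1 adds that within each band "randomization will be 1:1:1 allocation to the 2 L9LS arms and the placebo arm", so each arm of 75 holds "25 of weight 15-19 kg, 25 of weight 20-25 kg, and 25 of weight 26-30 kg".

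Section 4.3 describes the fixed paediatric doses as approximating "weight-based dosing of 5 mg/kg and 10 mg/kg, respectively, in a 30-kg child, and 10 mg/kg and 20 mg/kg, respectively, in a 15-kg child". Section 9.5.4 acknowledges the resulting 5-20 mg/kg range and plans an exploratory analysis of how dosage, "in terms of mg of L9LS per kg of subject body weight, affects the protective efficacy".

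Section 9.5.5 has no counterpart for safety. The number and percentage of subjects with AEs "will be summarized by dose arm along with the exact 95% CIs of the AE rate". In the efficacy study the dose arms are compared with control on solicited AEs, related AEs and SAEs. Neither weight band nor mg/kg is mentioned, and Section 9.5.9 plans no subgroup analyses. Year 2 uses the same methods (Section 9.5.1.1) and adds a comparison of all L9LS against all placebo (Section 4.1.1), which is coarser still.

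**The concern.** Safety is a primary objective in both parts of the trial. Within either dose arm, the lightest eligible child receives twice the mg/kg of the heaviest. The plan treats that spread as informative for efficacy and does not use it for safety.

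If reactions depend on exposure per kg, the children most likely to show them are the 15-19 kg band on 300 mg, who make up one third of their arm. Averaging them with the other two thirds can turn a visible excess into an unremarkable arm rate. Randomisation within bands already supplies a matched placebo group for each band, and the safety plan does not use it.

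**Working it through.** **The plan's own figure.** Section 9.2.1 gives the true AE rate at which an arm has a 90% chance of at least one event. The formula is 1 - 0.1^(1/n). For n = 6 it gives 0.319 and for n = 9 it gives 0.226, both as stated, and all cells of Table 3 reproduce. For the size of one weight band the same formula gives 0.536 (n = 3) and 0.088 (n = 25); for a full efficacy arm (n = 75) it gives 0.030.

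**mg/kg by band** (dose divided by the band limits):

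| Band | 150 mg | 300 mg |
|---|---|---|
| 26-30 kg | 5.0-5.8 | 10.0-11.5 |
| 20-25 kg | 6.0-7.5 | 12.0-15.0 |
| 15-19 kg | 7.9-10.0 | 15.8-20.0 |

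These are ranges. The two doses meet at 10 mg/kg (150 mg at 15 kg, 300 mg at 30 kg).

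**Dilution.** If only the lightest band has an excess, the arm rate is (25 × band rate + 50 × background)/75, so the arm excess is 25/75 of the band excess: a factor of 3.0 (9/3 = 3.0 in dose escalation). Example with an assumed 5% background and 30% in the band: (25 × 0.30 + 50 × 0.05)/75 = 13.3%, so the excess falls from 25 to 8.3 points.

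If the risk is graded, the factor is smaller. Take logit-linear risk from 10% at 0 mg/kg to 30% at 20 mg/kg, a slope of (-0.847 + 2.197)/20 = 0.0675. At mid-band weights of 28, 22.5 and 17 kg, 300 mg gives 10.7, 13.3 and 17.6 mg/kg and risks of 18.6%, 21.5% and 26.8%, with mean 22.3%. The factor is (26.8 - 10)/(22.3 - 10), about 1.4.

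**Power of simple comparisons.** Exact enumeration of two-sided Fisher tests at 0.05, with the excess only in the lightest 300-mg band:

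| Background / band rate (assumed) | 75 vs 75 | 25 vs 25, same band |
|---|---|---|
| 0% / 30% | 81% | 81% |
| 5% / 30% | 32% | 55% |
| 10% / 30% | 16% | 31% |

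**Simulation of the efficacy study.** There are 25 children per band and arm, weights are spread evenly within band, and the background risk is assumed to be 10%. Section 9.5.5 names no test for the arm comparisons, so two Fisher tests are used, with detection if either dose reaches 0.05. The alternatives are a trend over 0/150/300 mg that ignores weight, and a weight-band-stratified trend on mg/kg with placebo = 0.

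| Assumed risk | Arm-level Fisher | Arm-level trend | Stratified mg/kg trend |
|---|---|---|---|
| Graded, 30/35/40% at 20 mg/kg | 49/64/77% | 56/72/82% | 58/74/84% |
| 35/40% at or above 15 mg/kg only | 24/32% | 33/44% | 44/57% |

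Simulation error is about 2 points, and false-positive rates are about 5% for all three. In the 35% threshold case the 300-mg arm shows (25 × 0.35 + 50 × 0.10)/75 = 18%.

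**The case against.** The fixed-dose arm is a reasonable primary unit. The primary safety endpoint includes local reactions, and every child in the efficacy study receives two 1-mL injections whatever the arm (Section 6.2.4). Safety is also watched in ways that pooling does not touch:

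- individual line listings (Sections 9.5.5 and 9.5.10);
- a pause after one subject's unexpected related SAE, or one subject's two unexpected related grade 3 or greater AEs (Section 8.4.5);
- a halt after similar unexpected related grade 3 or greater events in two subjects (Section 8.4.6);
- at least one hour between subjects in dose escalation (Section 6.1.2.1), daily checks for expedited events and at least weekly data review (Section 8.4.2.3).

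Adults at 20 mg/kg IV form their own arm and must pass day 7 before any child is dosed. Finally, the threshold risk pattern is assumed, and under a graded risk the weight bands add only about 2 points beyond an arm-level trend.

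All of this stands as a limit on the point. A reader might infer that no output of any kind would reveal a problem at high mg/kg; the listings and the per-subject rules contradict that. The gap is in summary rates and comparisons. It does remain there: Section 9.5.5 does not name weight or mg/kg among the listing details, the per-subject rules address serious or severe events, and the adult 20 mg/kg arm differs in both route and age. The highest adult SC dose is 600 mg, about 10 mg/kg at 60 kg (Section 4.3).

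**Conclusion.** The safety analysis omits a dimension that the design randomises on and that the efficacy analysis uses. No planned summary or comparison isolates children at 15.8-20 mg/kg SC: 3 on L9LS in dose escalation and 25 in the efficacy study. The omission is worth correcting at low cost. It does not invalidate the safety analysis.

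Three stronger readings are not supported:

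- **A general three-fold loss.** Three-fold is the maximum, for the excess rate when a single band carries it. It is not a three-fold loss of power; with no background events, the arm-level and within-band Fisher tests have equal power.
- **That mg/kg is the stated reason for weight de-escalation.** The documents do not give the reason. It is a fair inference, and the point does not depend on it.
- **That weight bands drive most of the power gain.** Under graded risk, most of the gain comes from using a trend test (49/64/77% to 56/72/82%, then to 58/74/84%). Under the threshold pattern, about half comes from weight (33/44% to 44/57%).

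The documents give no AE rates by band, so all power figures rest on assumed risks. Over backgrounds of 0-10% and band rates of 20-40%, whole-arm Fisher power runs from 6% to 97% and within-band power from 9% to 97%.

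**What to change.** Add two items to Section 9.5.5:

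1. Descriptive AE tables by arm and randomisation weight band, with placebo children of the same band alongside, for the final analysis and for the DSMB. The DSMB version belongs in the closed, unblinded report only. It should not go to the day-7 reviews between arms: no unblinded reviewer is specified there, and tables of 3 against 3 could unblind a team that Sections 4.1 and 6.3.2 keep blinded.
2. One supportive analysis of 7-day AEs in the efficacy study, parallel to the mg/kg analysis in Section 9.5.4: a weight-band-stratified trend test, or a logistic model with weight band and mg/kg (placebo = 0).

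The arm-level summaries and comparisons stay primary. Weight is already recorded on day 0 and is the stratification factor, so no new data, larger sample or change to the efficacy error rate is needed. The cost is a few tables, cells too small for anything but description in dose escalation, and one more supportive test to interpret. No change of dose is implied.
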